4.2.1.2 Pharmacokinetic Endpoints

Plasma PK of MK-2060

The evaluation of MK-2060 PK will include determination of non-compartmental PK parameters including AUC₀₋₁₆₈, C_{max}, C₁₆₈, T_{max,terminal}, t_{1/2}, CL and V_z.

4.2.1.3 Pharmacodynamic Endpoints

aPTT and FXI activity (performed by Central Lab)

In order to assess PD, this study will include an assessment of aPTT prolongation levels (relative to baseline), and FXI activity levels, with assays being performed at a Central Laboratory. For PK/PD modeling, aPTT and FXI activity levels will be related to plasma exposure. The time points for PD data collection are based on the projected PK profile of MK-2060. Estimation of the aPTT effects of MK-2060 following multiple well-tolerated doses is an exploratory objective of this study.

4.2.1.4 Planned Exploratory Biomarker Research

4.2.1.4.1 Planned Genetic Analysis

Genetic variation may impact a participant's response to therapy, susceptibility to, severity, and progression of disease. Variable response to therapy may be due to genetic determinants that impact drug ADME; mechanism of action of the drug; disease etiology; and/or molecular subtype of the disease being treated. Therefore, where local regulations and IRB/IEC allow, a sample will be collected for DNA analysis from consenting participants.

DNA samples may be used for research related to the study intervention(s), the disease under study, or related diseases. They may also be used to develop tests/assays including diagnostic tests related to the disease under study, related diseases, and study intervention(s). Genetic research may consist of the analysis of 1 or more candidate genes, the analysis of genetic markers throughout the genome, or analysis of the entire genome. Analysis may be conducted if it is hypothesized that this may help further understand the clinical data.

In addition to studying variation across the human genome, CYP2C19 genotyping will be specifically investigated for association of variations with any clinical data.

4.2.1.5 Future Biomedical Research

The Sponsor will conduct FBR on specimens for which consent was provided during this study. This research may include genetic analyses (DNA), gene expression profiling (RNA), proteomics, metabolomics (serum, plasma), and/or the measurement of other analytes, depending on which specimens are consented for FBR.

Such research is for biomarker testing to address emergent questions not described elsewhere in the protocol and will only be conducted on specimens from appropriately consented participants. The objective of collecting/retaining specimens for FBR is to explore and identify biomarkers that inform the scientific understanding of diseases and/or their therapeutic treatments. The overarching goal is to use such information to develop safer, more effective drugs/vaccines, and/or to ensure that participants receive the correct dose of the correct drug/vaccine at the correct time. The details of FBR research are presented in Appendix 6.

4.3 Justification for Dose

The dosing regimen for MK-2060 (25 mg IV on days 1, 3, 5 of week 1 as loading phase, and 25 mg IV once in week 2) is the same as the first two weeks dosing of the high dose arm in the ongoing Ph2 study (PN007) and first two weeks of dosing of part 2 of MK-2060-004 in ESRD patients. This dose is projected to result in ~90% of participants with an aPTT of >1.5X baseline at Cmin during steady state (C168). The observed median Cmax is 93.4 nM and median Cmin is 44.8 nM at steady state after multiple dose of MK-2060 at 25 mg in ESRD patients receiving hemodialysis (MK-2060-004, incomplete data of Part 2) which achieved similar exposures as the projected steady state exposures of 25 mg in PN007 (median Cmax of 77 nM and median Cmin of 42 nM). As this is a Phase 1 assessment of MK-2060 in humans, and the PK, pharmacodynamic and safety profiles of the compound are still being evaluated, modifications to the dose or dosing regimen may be required to achieve the scientific goals of the study objectives and/or to ensure appropriate safety monitoring of the study participants. Details of allowed modifications are provided in Section 8.11.6.

4.3.1 Rationale for Dose Interval and Study Design

The ESRD/HD population is the target patient population for MK-2060, and a proportion of ESRD patients are taking antiplatelet therapy, such as clopidogrel. Dosing of MK-2060 with the 1 week loading regimen followed by 1 maintenance dose on Day 8 provides a duration of time where MK-2060 exposures are highest and FXI inhibition/aPTT prolongation is maximized (but not exceeding exposures observed in previous trials in ESRD/HD patients). With the slow clearance of MK-2060, there will be prolonged pharmacology during washout, during which time safety and bleeding-related AEs will continue to be monitored.

Each participant will be dosed and observed until discharge (~24 hours post-dose) for safety/tolerability. 24 hours is sufficient to monitor for initial safety/tolerability and local infusion site reactions and for systemic reactions to infusion. Following discharge, the following measures are being taken in this protocol to ensure the safety of study participants:

- Participants will be informed that they are taking an anticoagulant as a participant in this trial, and that this might increase the risk of bleeding as might occur in surgery, dental procedures, or strenuous exercise/contact sport activities.
- Participants will be excluded if they have planned significant dental procedures, including surgery, or other planned surgical procedures within duration of participation in the trial.
- Participants will be required to avoid scheduling any non-urgent/elective surgical or dental procedures, and to avoid strenuous physical activity and contact sport activities for the duration of the trial.
- Participants will be provided with an identification card and a medical alert bracelet, both of which identify them as participants in an anti-coagulant

research trial and, in the event of an emergency, will serve to notify healthcare providers that they might be at risk for provoked bleeding.

- If local lab aPTT values are > 3-fold above baseline, or local lab PT values are > 1.5 fold above baseline (at any time point), participants will be asked to remain in the clinic for at least 24 hours, and until aPTT/PT values are no longer increasing (upon retest) and at the discretion of the investigator.

Due to the physio-chemical properties of monoclonal antibody (mAb) therapeutics, transfer to the seminal compartment and subsequent vaginal uptake of a mAb is essentially zero, as demonstrated in rabbits, monkeys, and humans [Breslin, W. J., et al 2014], [Moffat, G. J., et al 2014], and [Sohn, W., et al 2015]. In addition, in an embryofetal developmental toxicity study in pregnant rabbits administered MK-2060, there was no evidence of embryofetal lethality or teratogenicity up to 120 mg/kg/day (the highest dose evaluated; 1 dose QW for 2 weeks) providing an estimated systemic exposure margin of 234-fold the observed AUC0-168hr of 63 day• μ g/mL after multiple 60-minute IV infusion doses of 25 mg IV at steady state in ESRD patients. Therefore, there is no risk to pregnant partners of male participants receiving MK-2060, and male contraception during clinical studies with MK-2060 is not warranted.

4.4 Beginning and End-of-Study Definition

The overall study begins when the first participant (or their legally acceptable representative) provides documented informed consent. The overall study ends when the last participant completes the last study-related contact, withdraws consent, or is lost to follow-up (ie, the participant is unable to be contacted by the investigator).

A study may be paused during review of newly available preclinical/clinical safety, PK, pharmacodynamic, efficacy, or biologic data or other items of interest, prior to a final decision on continuation or termination of the study. It may be necessary to keep the study open for gathering/reviewing of additional supportive data to optimally complete the objective(s) of the study. If necessary, the appropriate amendment(s) to the protocol and/or appropriate communication(s) will be generated. If the decision has been made to end the study following this review period, the study end will be defined as the date of the Sponsor decision, and this end of study date supersedes the definitions outlined above. The Competent Authority(ies) and IRB(s)/IEC(s) will be apprised of the maximum duration of the study beyond the last participant out and the justification for keeping the study open.

4.4.1 Clinical Criteria for Early Study Termination

There are no prespecified criteria for terminating the study early.

5 STUDY POPULATION

Male and Female participants with ESRD on HD between the ages of 18 and 80 years (inclusive) will be enrolled in this study.

Prospective approval of protocol deviations to recruitment and enrollment criteria, also known as protocol waivers or exemptions, is not permitted.

5.1 Inclusion Criteria

A participant will be eligible for inclusion in the study if the participant meets all of the following criteria:

Type of Participant and Disease Characteristics

1. ESRD maintained on stable outpatient HD regimen at a healthcare center for > 3 months prior to dosing, using an established and normally functioning, regular flow, uninfected mature AV fistula or AV graft and skin consistent with standard chronic HD access injuries, and HD stability defined as $Kt/V \geq 1.2$ within 3 months prior to dosing.
2. On HD regimen at least 3 times per week for a minimum of 3 hours per dialysis session, using a complication-free well-maintained AV fistula or AV graft, expected and plan to continue this throughout and at least up to poststudy.
3. Is taking clopidogrel for a minimum of 2 weeks prior to the first dosing of MK-2060 administration and will continue to take clopidogrel for at least the duration of MK-2060 treatment.
4. Have a Body Mass Index (BMI) ≥ 18 and $\leq 45 \text{ kg/m}^2$. BMI = weight (kg)/height (m)². Dry weight (body weight after hemodialysis) should be used for BMI calculations.
5. Baseline health is judged to be stable based on medical history, physical examination, vital sign measurements and ECG performed prior to treatment allocation.
6. Liver function test (serum alanine aminotransferase [ALT] and aspartate aminotransferase [AST]) must be equal to or below 1.5X upper limit of normal (ULN) and deemed not clinically significant by the investigator.
7. Be willing to comply with the trial restrictions (see Section 5.3) for a complete summary of trial restrictions).

Demographics

8. Is male or female, from 18 years to 80 years of age inclusive, at the time of providing informed consent.

Female Participants

9. A female participant is eligible to participate if she is not pregnant or breastfeeding, and at least one of the following conditions applies:
 - Not a WOCBP

OR

- A WOCBP and:
 - Uses an acceptable contraceptive method, or be abstinent from heterosexual intercourse as their preferred and usual lifestyle (abstinent on a long-term and persistent basis), as described in Appendix [5] during the intervention period and for at least 96 days after the last dose of study intervention. The investigator should evaluate the potential for contraceptive method failure (ie, noncompliance, recently initiated) in relationship to the first dose of study intervention. Contraceptive use by women should be consistent with local regulations regarding the methods of contraception for those participating in clinical studies
 - Has a negative highly sensitive pregnancy test (urine or serum as required by local regulations) within 76 hours before the first dose of study intervention. If a urine test cannot be confirmed as negative (eg, an ambiguous result), a serum pregnancy test is required. In such cases, the participant must be excluded from participation if the serum pregnancy result is positive. Additional requirements for pregnancy testing during and after study intervention are in Section 8.5.5.
 - Medical history, menstrual history, and recent sexual activity has been reviewed by the investigator to decrease the risk for inclusion of a woman with an early undetected pregnancy.

Informed Consent

10. The participant (or legally acceptable representative) has provided documented informed consent/assent for the study. The participant may also provide consent/assent for FBR. However, the participant may participate in the study without participating in FBR.

Additional Categories

Consent must be documented by the participant's dated signature or by the participant's legally acceptable representative's dated signature on a consent form along with the dated signature of the person conducting the consent discussion.

A copy of the signed and dated consent form should be given to the participant before participation in the trial.

The initial informed consent form, any subsequent revised written informed consent form and any written information provided to the participant must receive the IRB/ERC's approval/favorable opinion in advance of use. The subject or his/her legally acceptable representative should be informed in a timely manner if new information becomes available that may be relevant to the participant's willingness to continue participation in the trial. The communication of this information will be provided and documented via a revised

consent form or addendum to the original consent form that captures the subject's dated signature or by the participant's legally acceptable representative's dated signature.

Specifics about a trial and the trial population will be added to the consent form template at the protocol level.

The informed consent will adhere to IRB/IEC requirements, applicable laws and regulations and Sponsor requirements.

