Orthostatic VS	X			X	X	X	X	X	X			X	X						Sec. 8.3.2.2 To be done at predose on Days 1, 3, 5 and 8. To be done before start of dialysis on Days -3 and 15.	
12-lead ECG	X			X	X	X	X	X	X		X					X		Sec. 8.3.3 To be done at predose on Days 1, 3, 5 and 8		
Serum FSH - (WONCBP only)	X																			
Serum or Urine Pregnancy test (WOCBP only)	X			X													X			
HIV, hepatitis B and C screen	X																			
Drug Screen and Alcohol Breath Test	X				X														Appendix 2 DS and alcohol breath test is mandatory at Screening and predose; any additional DS and alcohol breath tests are conducted per site SOP Blood or saliva DS may be used for anuric participants	

Study Period:	Screen-ing	Run-in ^a													Intervention					Intervention Notes
		Day -14	Day -7	Day -3	Day 1	Day 2	Day 3	Day 5	Day 8	Day 9	Day 10	Day 12	Day 15	Day 21	Day 29	Day 35	Day 49	Day 67	Day 104	
Scheduled Day																				
Hematology	X			X	X		X		X		X		X		X	X	X	X	X	Sec. 8.3.5 Appendix 2 To be done predose on Days 1, 3 and 8
aPTT/PT at Local Lab	X				X		X	X	X	X	X	X	X	X	X		X		X	Sec. 8.3.5 Appendix 2 Days 1, 3, 5 & 8: predose, 1h and 12h.
Chemistry ^c	X			X	X		X		X		X		X		X	X	X	X	X	Sec. 8.3.5 Appendix 2 To be done at predose on Days 1, 3 and 8
Hemoccult Test ^d				X		X		X	X		X		X		X		X			Sec. 8.3.5, 8.11.5
AE/SAE review	X	X	X	X	X	X	X	X	X	X	X	X	X	X	X	X	X	X	X	Sec 8.5, Appendix 3
Pharmacokinetics																				
Blood for Plasma MK-2060 Assay ^{e,f}					X	X	X	X	X	X	X	X	X	X	X	X	X	X	X	Sec. 8.7 Days 1 & 8: predose, 1h, 12h. Days 3 &5: predose, 1h. See footnotes e, f
Blood for Clopidogrel Assay ^{e,f}		X	X	X	X	X	X	X	X											Sec. 8.7 See footnote e, f.
Pharmacodynamics																				
Blood for PT/aPTT/ FXI Activity by Central Lab ^f					X	X	X	X	X	X	X	X	X	X	X	X	X	X	X	Sec. 8.8, Days 1 & 8: predose and 1h (within 15 min of end of infusion). Days 3 &5: predose
Biomarkers																				
Blood for Plasma ADA ^f					X								X			X		X	X	Sec. 8.9.3 Day 1: predose
Blood (DNA) for Planned Genetic Analysis					X															See section 8.8

Study Period: Scheduled Day	Screen-ing	Intervention													Post-study	Intervention Notes			
		Day -14	Day -7	Day -3	Day 1	Day 2	Day 3	Day 5	Day 8	Day 9	Day 10	Day 12	Day 15	Day 21	Day 29	Day 35	Day 49	Day 67	Day 104

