8.11.2 Treatment Period

Refer to the Schedule of Activities (Section 1.3) and Administrative and General Procedures (Section 8.1).

After all predose procedures have been completed, participants will be assigned a unique allocation number in a computer-generated allocation schedule.

Participants will be administered study drug as indicated in Section 6. Participants who on Day 1 have a significant acute illness or fever prior to the administration of study drug may be rescheduled.

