- Postdose evaluations: weight (Day 104), serum or urine pregnancy test (Day 104): use windows indicated in [Table 7](#).
- Study intervention administration: +/- 1 hour relative to time of dosing on Day 1.
- Run-in (Day -14 to Day -3 Visits): ± 1 day is allowed.

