10.2 Appendix 2: Clinical Laboratory Tests

- The tests detailed in [Table 8](#) will be performed by the local laboratory.
- Protocol-specific requirements for inclusion or exclusion of participants are detailed in Section 5 of the protocol.
- Additional tests may be performed at any time during the study as determined necessary by the investigator or required by local regulations.

Table 8 Protocol-required Safety Laboratory Assessments

Laboratory Assessments	Parameters							
Hematology	Platelet Count	RBC Indices: MCV MCH Reticulocytes	WBC count with Differential: Neutrophils Lymphocytes Monocytes Eosinophils Basophils					
	RBC Count							
	Hemoglobin							
	Hematocrit							
Chemistry ^a	BUN	Potassium	AST/SGOT	Total bilirubin (and direct bilirubin, if total bilirubin is above the ULN)				
	Albumin	Bicarbonate	Chloride	Phosphorous				
	Creatinine	Sodium	ALT/SGPT	Total Protein				
	Glucose	Calcium	Alkaline phosphatase					
Other Screening Tests	
• aPTT, PT (collection according to the trial schedule of activities Section 1.3 for aPTT and PT collected at local lab)• FSH (as needed in WONCBP only)• Serum or urine β human chorionic gonadotropin (β hCG) will be carried out on Day 1 predose. At all other timepoints urine or serum pregnancy test will be carried out (as needed for WOCBP) (Serum β hCG pregnancy test will be carried out if there is a positive urine test)• alcohol breath test and drug screen (to include at minimum: amphetamines, cocaine, opiates, cannabinoids and benzodiazepines)• Serology (HIV antibody, HBsAg, and hepatitis C virus antibody)]							
ALT=alanine aminotransferase; AST=aspartate aminotransferase; BUN=blood urea nitrogen; FSH=follicle-stimulating hormone; [HBsAg=hepatitis B surface antigen]; hCG=human chorionic gonadotropin; [HIV=human immunodeficiency virus]; MCH=mean corpuscular hemoglobin; MCV=mean corpuscular volume; RBC=red blood cell; SGOT=serum glutamic-oxaloacetic transaminase; SGPT=serum glutamic-pyruvic transaminase; ULN=upper limit of normal; WBC=white blood cell; WOCBP=women of childbearing potential; WONCBP=women of nonchildbearing potential								
^a Fasting: Participants should fast for at least 4 hours prior to glucose measurement.								

The investigator (or medically qualified designee) must document their review of each laboratory safety report.

10.3 Appendix 3: Adverse Events: Definitions and Procedures for Recording, Evaluating, Follow-up, and Reporting

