10.8 Appendix 8: Blood Volume Table

	Prestudy	Treatment Periods	Poststudy	Total Collections	mL Per Collection	Total mL/Test
Laboratory Safety Tests	2	9	1	12	12.5	150
HIV/Hepatitis Screen	1			1	5	5
FSH (Females only)	1			1	3.5	3.5
Serum β-hCG pregnancy test (Females only)	2		1	3	3.5	10.5
Blood (DNA) for genetic analysis		1		1	8.5	8.5
Blood for PT and aPTT at local lab	1	19	1	21	3	63
Blood for plasma ADA and MK-2060		4	1	5	2.7	13.5
Blood for MK-2060 only		16		16	1.8	28.8
Blood for Clopidogrel Assay	3	5		8	4	32
Blood for PT, aPTT, FXI activity by central lab		16	1	17	8.1	137.7
Total Blood Volume per Male Participant^a						438.5 mL
Total Blood Volume per Female Participant^a						452.5 mL

^a If additional pharmacokinetic/pharmacodynamic and/or safety analysis is necessary, additional blood (no more than 50 mL in total) may be obtained.

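### The pre-dose pregnancy test is timed inconsistently: the schedule and its visit window allow a test about 96 hours old at first dose, against a 76-hour entry limit

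*Combined protocol and SAP*

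**What the plan says.** Several places bear on when the last pregnancy test before dosing is done.

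- Section 5.1, criterion 9: a negative highly sensitive test is needed, "urine or serum as required by local regulations) within 76 hours before the first dose of study intervention".
- Section 1.3, Schedule of Activities, row "Serum or Urine Pregnancy test (WOCBP only": as extracted, the row has marks at Screening and Day -3, none at Day 1, and one late mark for the poststudy test.
- Section 10.8 (Appendix 8), row "Serum β-hCG pregnancy test (Females only": two collections prestudy, none in the treatment period, one poststudy, at 3.5 mL each.
- Section 10.2 (Appendix 2), Table 8: "Serum or urine β human chorionic gonadotropin (β hCG) will be carried out on Day 1 predose".
- Section 8.11.5: "Run-in (Day -14 to Day -3 Visits): ± 1 day is allowed".
- Section 8.11.2: "Participants who on Day 1 have a significant acute illness or fever prior to the administration of study drug may be rescheduled". Nothing is said there about the age of the pregnancy test.

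Criterion 9 adds: "Additional requirements for pregnancy testing during and after study intervention are in Section 8.5.5". Section 8.5.5 deals only with reporting and following up pregnancies and breastfeeding exposure; it contains no testing requirement. Section 5 rules out waivers of entry criteria.

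**The concern.** Section 8 makes adherence to the schedule mandatory, so sites will plan visits from it. If the schedule and its window can produce a test older than the entry criterion allows, a site may do everything the schedule asks and still arrive at Day 1 with a woman who does not qualify. She then needs an unplanned test, or she is dosed in breach of criterion 9.

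The check on the day may not catch this. The schedule's note on eligibility review says that only certain criteria are reviewed again before allocation on Day 1, and does not list them. The 24-hour predose window in Section 8.11.5 names aPTT, PT and the drug screen but not the pregnancy test.

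The matter is new to this study relative to MK-2060-004, which Section 2.2.2 describes as enrolling men and women of non-childbearing potential. This protocol admits women of childbearing potential and asks for a review to reduce the risk of including an early undetected pregnancy.

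**Working it through.** The 76-hour limit is set, not derived, so there is no plan figure to reproduce. The check is which visit the schedule means, and how old the test is at dosing.

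**Which visit.** The schedule's columns run Screening, Day -14, Day -7, Day -3, Day 1, and so on. The pregnancy row has marks in the first and fourth columns. Other rows confirm that the fourth column is Day -3:

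- Orthostatic vital signs are also marked in the fourth column, and their note names Day -3.
- The drug screen has one more blank cell and falls on Day 1, matching its predose note.
- Hematology falls on Screening and Day -3 (2), nine days from Day 1 to Day 67, and Day 104 (1). Appendix 8 gives 2 + 9 + 1.
- The clopidogrel assay gives 3 run-in and 5 treatment samples, as in Appendix 8.

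Appendix 8 lists the DNA sample, taken only on Day 1, under the treatment period. Day 1 samples are therefore not counted as prestudy, and the two prestudy pregnancy samples are Screening and one run-in visit.

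**Day numbering.** Section 8.11.1 starts the run-in about 14 days before allocation, which puts Day -14 fourteen days before Day 1, with no Day 0. The dialysis pattern agrees: if Day 1 is a Monday, Days 1, 3, 5 and 8 are Mon, Wed, Fri, Mon, and Days -14, -7 and -3 are Mon, Mon, Fri.

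**Age of the test.** Age in hours = days from test to first dose × 24, taking test and dose at the same clock time.

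| Test taken | Days before dose | Age at dose | Against 76 h |
|---|---|---|---|
| Day -4 (early edge of window) | 4 | 4 × 24 = 96 h | 96 − 76 = 20 h over |
| Day -3 (nominal) | 3 | 3 × 24 = 72 h | 76 − 72 = 4 h inside |
| Day -2 (late edge of window) | 2 | 2 × 24 = 48 h | 76 − 48 = 28 h inside |
| Day 1 predose (Appendix 2) | 0, or at most 1 if the 24-hour predose laboratory window applies | at most 24 h | inside |

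**Clock time.** The nominal visit has only 4 h of slack. If the dose is given 5 h later in the day than the Day -3 test, the age is 72 + 5 = 77 h, which is out of limit.

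**Postponed Day 1.** Each day adds 24 h. A nominal Day -3 test followed by a one-day postponement is 72 + 24 = 96 h old.

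**The case against.** The strongest reply is that the limit does its own work. Criterion 9 is explicit, runs to the first dose and cannot be waived. Under Section 8.1.2 the investigator reviews all criteria, and the schedule marks an eligibility review at Day -3 and again at Day 1. A visit window cannot relax an entry criterion, and a site following Appendix 2 meets the limit. All of this stands. A reader might infer that the 76-hour limit itself is unreliable; the documents do not support that, because a 96-hour-old test makes the woman ineligible until she has a valid one. What remains is that the schedule, its window and Appendix 2 do not lead a site to the same test.

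A second reply is that the table is damaged in extraction. The pregnancy row's last mark falls under Day 49, although Section 8.11.5 puts that test on Day 104, and the local infusion reaction row appears to start a column early. A one-column slip would move the Day -3 mark to Day 1. The published table should be checked, but a slip does not explain the two prestudy and zero treatment-period samples in Appendix 8. Appendix 8 counts blood only, so it cannot exclude a urine test on Day 1. It does leave no volume for a serum test that day, which Appendix 2 permits.

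Third, Day -4 is the worst case. On a thrice-weekly pattern it is not a dialysis day, and the Day -3 visit includes on-site dialysis. That makes the early edge less likely, but the window still allows it.

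Three further inferences should be resisted:

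- That Section 8.11.2 permits dosing after a postponement without a new test. It is silent, and criterion 9 still runs to the actual first dose.
- That the Section 7.1 rule on a positive serum test has nothing to trigger it during dosing. Appendix 2 provides for tests at other timepoints as needed and allows additional tests at any time.
- That a Day 0 exists, so that even the nominal visit fails. That numbering puts the run-in visits off the dialysis pattern and conflicts with Section 8.11.1.

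**Conclusion.** The point holds as an inconsistency in timing. The schedule and Appendix 8 put the last pre-dose test at Day -3, and Appendix 2 puts it on Day 1. The permitted visit window allows a test about 96 h old at first dose, 20 h beyond the criterion 9 limit; the nominal visit leaves about 4 h. The result rests on there being no Day 0, on test and dose at the same clock time, and on the Day -3 column reading, which Appendix 8 supports.

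The consequence is limited. It concerns eligibility and participant protection for those women of childbearing potential who enter among up to 12 participants. They must also use acceptable contraception or be abstinent, and their menstrual and recent sexual history is reviewed. No endpoint or analysis method changes, and the safety population is everyone dosed. It should still be corrected, because following the schedule can lead to a breach of an entry criterion that nobody may waive.

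**What to change.** - Reconcile criterion 9, the schedule row and its visit window, Appendix 2 and Appendix 8 so that they give one timing for the last pre-dose test. Which timing is for the sponsor to decide.
- State in Section 8.11.5 that the one-day run-in window does not override the criterion 9 limit, and in Section 8.11.2 that a postponed Day 1 does not either. The limit runs to the actual first dose.
- Correct the reference from criterion 9 to Section 8.5.5: point to where testing requirements are given, or remove it.

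The cost is amendment wording and at most one extra urine or 3.5 mL serum test. Participants already report to the unit the evening before dosing (Section 8.1.11). If a scheduled serum test is added rather than moved, the pregnancy row becomes 4 × 3.5 = 14.0 mL and the female total 452.5 + 3.5 = 456.0 mL. The ceiling of about 453 mL in Section 8 would then need updating too. A moved test or a urine test leaves the total unchanged.
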